### **4.0 ELIGIBILITY**

The UI Health Department of Emergency Medicine serves a diverse population in Chicago and is a Level II trauma center located within the Illinois Medical District.

All patient recruitment will be completed in the UI Health Department of Emergency Medicine (ED). ED study personnel will approach patients who meet inclusion criteria for the study. Study personnel will be available on rotating shifts (including days, nights, and weekends) in order to facilitate ongoing patient recruitment and enrollment. Individuals deemed eligible will be consented and sign a written consent with HIPAA authorization and have baseline data collection. The research assistants (RAs) will inform patients that the research is being conducted to improve hypertension knowledge and blood pressure control by facilitating primary care connections and to determine if the ED can help people reach goals of treatment.

#### **4.1 Inclusion Criteria:**

Inclusion criteria: Stage 1 Hypertension- Elevated Blood Pressure of  $\geq 140/90$  and  $\leq 180/110$  at time of discharge from ED; Verbal fluency in English or Spanish; Age 18 to 75 years.

#### **4.2 Exclusion Criteria:**

Exclusion criteria: Unable to verbalize comprehension of study or impaired decision making or documented dementia; Lives outside Chicago communities or plans to move from Chicago area within the next year; Pregnant or trying to get pregnant; COVID-19 positive.

#### **4.3 Vulnerable Populations:**

Study participants will be patients with uncontrolled/undiagnosed HTN in underrepresented groups presenting to the emergency department. ED engagement and early risk assessment/stratification is aimed to be a cost-effective, feasible, and minimally invasive innovation to help close health disparity gaps in HTN.

#### **Collaborating Sites:**

There are no collaborating sites.

### **5.0 SUBJECT ENROLLMENT**

[figure not shown]
In order to minimize the possibility of coercion or undue influence on potential subjects, subjects will only be approached for study consent after they have completed their evaluation in the emergency department and have been identified for discharge. Subjects will also be

informed that participation is voluntary and will not affect their relationship with the university/hospital if they decline to participate. Also, patients that are being cared for by the PI or key personnel will not be approached and consented by that individual but rather another member of the study team. Subjects will initially be identified by review of the tracking board listing in the department. The tracking board displays the patients' last name, room number, age, and vital signs. If patients meet the BP requirement (BP  $\geq$  140/90 and  $\leq$  180/110) and are slated for discharge from the emergency department, then a clinical EMT will approach the attending physician caring for the patient for preliminary review of exclusion criteria. Eligible participants will be approached by the clinical EMT with an iPad. The research assistant will communicate with the potential participant via the iPad. The consent form will be electronic to avoid possible contamination. Additionally, participants will be informed that a thank you letter will be mailed to their home after completion of the study. At no time will any information about refusals to participate be placed in the subjects' medical record. All data will be entered into electronic database (REDCap). There will be no paper charts/data entry. This will minimize the potential for loss of information and breech of privacy. All of this information will be handled in accordance with HIPAA guidelines. We do not expect subjects to experience discomfort with the collection of the minimally invasive clinical measures collected.

## **6.0 STUDY DESIGN AND PROCEDURES**

Human Subjects Involvement: The proposed study is a randomized, controlled trial focused on a high-risk ED population with evidence of moderately elevated blood pressures ( $\geq$ 140/90 and  $\leq$ 180/110). 770 ED patients (predominately African-American and Latino patients, based upon the demographics of the UI Health patient population) will be randomized to one of two arms: 1.) usual care (preprinted discharge instructions and a 48-72 hour referral to our FQHC program or assigned provider as appropriate) or 2) the ED-initiated Educational and Empowerment (E) intervention and PACHTc intervention followed by 48-72 hour referral to our FQHC (or assigned health center). There will be 385 subjects in each arm.

**Figure 1. Study Design**

The E intervention (arm 2) consists of a series of risk assessment tools (surveys, video, and minimally invasive bedside assessments) designed to be efficient, patient-centered and educational for participants in an emergency department setting. Through the intervention, participants will learn more about hypertension management and secondary complications associated with uncontrolled BP, such as subclinical heart disease.

Subclinical heart disease refers to the presence of early echocardiogram changes seen on limited bedside echocardiograms often as a result of uncontrolled hypertension. These changes include diastolic dysfunction and left ventricular hypertrophy. Many of these changes can be reversible with hypertension control. Study participants will not be diagnosed with subclinical heart disease in the ED. Instead participants will be shown limited bedside echocardiogram video clips of gender matched echocardiograms with subclinical changes as a part of an empowerment tool of the study.

Using Atherosclerotic Cardiovascular Disease (ASCVD) risk score calculators preloaded on study iPads, participants will have their risk score calculated by entering their age, tobacco status (Y/N), Systolic BP, Cholesterol/HDL, and BP treatment (Y/N). Point of care cholesterol/HDL measurement will be obtained using the Polymer Technology Systems CardioCheck PA Analyzer, which analyzes up to 4 cholesterol types with a single fingerstick of blood and is CLIA-waived and FDA approved. Trained nurse practitioners and emergency medical technicians will be performing the cholesterol tests.

Additionally, all participants in arm 2 will receive a Post-Acute Care Hypertension Transition Consultation (PACHTC) with a clinical pharmacist or APN. To ensure consistency throughout the trial, the PACHTC will be standardized and interchangeable between the clinical pharmacists and APNs. During the day, the on-site ED clinical pharmacist will provide consultations. During evening and weekend hours, consultations will be provided by the APN located in the ED Clinical Decision Unit (CDU).

Finally, all participants randomized to arm 2 will receive an FDA-approved HBPM kit that includes the Nokia wireless (self-inflating) BPM monitor and Health Mate mobile app. Participants without a mobile device will be provided one for the study.

The app automatically launches when the patient slips on the cuff and turns on the monitor to measure his/her BP. All BP readings automatically sync with the app, which creates an easy-to-understand chart of all the measurements and provides participants with instant color-coded feedback based on AHA recommendations for hypertension. Synced data are automatically uploaded from the mobile app to the iCardia server of our study.

Participants will be shown how to use the BP monitor and app by a clinical EMT, view a standardized 2-minute instructional video, and asked to confirm/demonstrate that they understood how to use the device and app using the teach-back method prior to leaving the ED. Participants will be asked to check their BP at home, preferably daily but a minimum of twice per month, and use the mobile app to view their data. The EMT will set-up daily or bi-weekly automatic reminders in each participant's mobile app that will prompt them to measure their BP at a preferred time.

In case of missed measurements for 1 consecutive week, participants will receive one text-message per day through the iCardia platform for four consecutive days until they complete a BP measurement. In case of missed measurements for 14 consecutive days, participants will be contacted by phone by the RA's. All data will be remotely monitored by the RA's through the iCardia platform. The patient-centered benefit of HBPM monitoring has been repeatedly shown and is recommended as an important component of HTN management. HBPM has been shown to improve adherence to medications, induce healthy lifestyle changes, and aid in optimizing of treatment. In addition, use of the HBPM values will serve as a safety feature to avoid pushing BP too low in study participants.

Additionally, participants will be sent behavioral change text messages. The text messages come from a pool of validated messages chosen by the investigators. They promote medication adherence and BP measurement adherence. The message database will be submitted along with this document. Participants will receive 3 behavioral text messages per week at a time of their preference, in addition to the app notifications they receive each day to monitor their blood pressure. Text messages will be programmed in iCardia by research staff.

The Usual Care group (Arm 1) will receive preprinted discharge instructions and an outpatient referral. This group represents standard of care. All other interventions in arm 2 are research activities.

**Table 1: Intervention Components by Arm \***

Arm 1: Usual Care (N=385)				
Arm 2: E Intervention (N=385)				
Intervention Components by Arm	Baseline	Quarterly	Mid-point	End
Location	ED	Phone	UI-Health Suite 1600	UI-Health Suite 1600
Time Point in Months (0=ED discharge)	0	1, 3, 5	3	6
Duration	10-20 min	5 min	10-20 min	20 min
BP Measured	1, 2		1, 2	1, 2
Clinical Data (from med chart)	1, 2			

Atherosclerotic Cardiovascular Disease (ASCVD) Risk Score	1,2			1,2
Hypertension Knowledge Assessment	1, 2			1, 2
Modified Morisky Scale	1, 2	1, 2	1, 2	1, 2
Patient Activation Measurements Survey (PAM)	1, 2	1, 2	1, 2	1, 2
Verify patient contact info	1, 2	1, 2	1, 2	
Bedside Echocardiogram Education	2			
Hypertension Education Video	2			
PACT-Hypertension (Pharmacy) Consultation:	2			
Home BP Monitoring Training and Reminders	2	2	2	

\*We may ask participants to return for a follow up at one year post-enrollment at which time all assessments and surveys performed at recruitment will be repeated.

#### **Details of ED Screening (risk assessment, both arms)**

**BP Measurement:** Prior to randomization all participants will be screened using a standardized 5- point pain scale with 5 indicating severe pain and 0 no pain. Participants with moderate to severe pain (3-5) will not be randomized until their pain scale is improved (0-2). Participants will then have a standard BP measurement taken (as per AHA guidelines) to ensure consistency and standardization of BP measurements throughout the trial.

The blood pressure measurements will be obtained using standard monitors currently available in our Emergency Department: Welch Allyn, Model VSM 6000 series, Configuration Number: NIBP, Pulse Rate, SPO2, Temp, Hardware Version P3, Software Version 1.71.03.

The blood pressure measurement protocol based on the AHA guidelines are as follow:

1. The patient will be asked to remove all clothing that covers the location of cuff placement.

2. The individual will be comfortably seated, with the legs uncrossed, and the back and arm supported, such that the middle of the cuff on the upper arm is at the level of the right atrium (the mid-point of the sternum).
3. The patient will be instructed to relax as much as possible and to not talk during the measurement procedure. The patient will be asked to sit quietly for 5 minutes before the first reading is taken.
4. A minimum of three readings will be taken and the average of the last two readings will be used to record the measurement. There will be intervals of at least 1 minute between readings.
5. If there is >4 mm Hg difference between the second and third readings, additional (one or two) readings will be obtained and then the average of the two closest readings will be used.

***Atherosclerotic Cardiovascular Disease (ASCVD) Risk Score:*** Using ASCVD Risk Score calculators preloaded on study iPads, participants will have their risk score calculated by entering their age, tobacco status (Y/N), Systolic BP, Cholesterol/HDL, and BP treatment (Y/N). Point of care cholesterol/HDL measurement will be obtained using the Polymer Technology Systems CardioChek PA Analyzer, which analyzes up to 4 cholesterol types with a single fingerstick of blood and is CLIA-waived and FDA approved.

***Hypertension Knowledge Survey (all arms):*** The hypertension knowledge survey is a 10-item, validated tool developed to assess hypertension knowledge in low literacy patient populations. The scale assesses respondents' knowledge in defining hypertension, lifestyle, and behaviors that may affect BP levels, and the long-term consequences of HTN. The survey has been validated in an urban population that included a high proportion of black and Latino patients. Scores are categorized into tertiles that indicate low ( $\leq 7$ ), medium (8), or high (9-10) levels of HTN knowledge.

***Modified Morisky Scale Health Survey and Patient Activation Measurement Survey (PAM) (all arms):*** The modified Morisky scale is a validated 4-item instrument to assess self-reported patient adherence related to antihypertensive medication. The modified Morisky scale provides a total score with a range of 0 to 4, with higher scores indicating lower adherence to medication. The scores of the modified Morisky scale can be classified as low compliers (3-4), medium

compliers (1-2) and high compliers (0) based on its criterion validity with BP control. The Patient Activation Measurement Survey (PAM) is a 10-item instrument that measures level of engagement (activation) and has been used and validated in HTN interventions with higher scores meaning better self-care behaviors. The surveys will be administered by RAs at the time of enrollment and at 3, 6, and 12 months during the in-person visit.

### **Details of Intervention Components**

**HTN Educational Video.** The video will educate participants in arm 2 about high BP, how it is diagnosed, and the importance of treating it to prevent secondary complications. Based upon the existing literature overall HTN knowledge is extremely low among minority populations. Participants will review a 3-5 minute video on HTN, The customized video will be bi-lingual and culturally sensitive. After the video participants will complete a short touch-screen self-assessment with real-time computerized feedback.

**Visual Echocardiogram Image Clips:** We are using visual images of gender-matched echocardiograms as a tool to educate and motivate patients to change their behavior to improve their BP. We have found that **the real time visualization of cardiac ultrasound images with active discussion of findings is a significant patient motivator and empowerment tool**, and was a significant factor in the success of a previous pilot study. (Figure 2)

[figure not shown]

Figure 2. Images of a patient with mild to moderate diastolic dysfunction as evidenced by a normal E/A ratio, but an e' lateral mitral valve annular velocity  $< 10$  cm/s. Patients are better informed about consequences of untreated HTN when they can visualize the effects of HTN on the heart.

**Smartphone-enabled BP monitoring Kit:** All participants randomized to the intervention group will receive an FDA-approved home BP monitoring kit that includes the Nokia wireless (self-inflating) BPM monitor and Health Mate mobile app. The app automatically launches when the

patient slips on the cuff and turns on the monitor to measure his/her BP. All BP readings automatically sync with the app, which creates an easy-to-understand chart of all the measurements and provides participants with instant color-coded feedback based on AHA recommendations for hypertension. Synced data are automatically uploaded from the mobile app to the iCardia server of our study. Participants will be shown how to use the BP monitor and app by RAs, view a standardized 2-minute instructional video and asked to confirm/demonstrate that they understood how to use the device and app using the teach-back method prior to leaving the ED. Participants will be asked to check their BP at home daily and use the mobile app to view their data. The EMT's will set-up daily automatic reminders in each participant's mobile app that will prompt them to measure their BP at a preferred time. In case of missed measurements for three consecutive days, participants will receive one text-message per day through the iCardia platform for four consecutive days until they complete a BP measurement. In case of missed measurements for 7 consecutive days, participants will be contacted by phone by the RA's. Participants will also receive 3 behavioral text messages per week that are aimed at improving medication adherence and BP measurement adherence. All data will be remotely monitored by the RA's through the iCardia platform. Participants will be informed that the Health Mate app is not a telemonitoring app and in the event the participant is experiencing a hypertensive crisis ( $>180/120$ ) they must contact a physician immediately. The patient-centered benefit of home BP monitoring has been repeatedly shown and is recommended as an important component of HTN management. Home BP monitoring has been shown to improve adherence to medications, induce healthy lifestyle changes, and aid in optimizing of treatment. In addition, use of the home BP monitoring values will serve as a safety feature to avoid pushing BP too low in study participants.

**PACHT-c:** All participants randomized to the E intervention will have a focused consultation with either a clinical pharmacist or an APN. To ensure consistency throughout the trial, the PACHT-c intervention will be standardized and interchangeable between the clinical pharmacists and APNs. During the day, the on-site ED clinical pharmacist will provide consultations. During evening and weekend hours, consultations will be provided by the APN located in the ED Clinical Decision Unit (CDU). The CDU is open 24 hours a day, 7 days a week. During this consultation, the pharmacist/APN repeats the BP measurement; reviews the screening

assessments; and reviews general principles of BP control including nutrition, exercise, and smoking cessation. BP will be managed according to the current published guidelines available regarding initiation of first-line antihypertensive medications. Patients with BP  $\geq 140/90$  mmHg may be started on antihypertensive medications by the provider during the consultation if appropriate. All PACTH-c clinic notes will be accessible in the EMR, which is shared between both the ED and our FQHC, Mile Square Health Center. No tests will be ordered during the pharmacy follow-up.

[figure not shown]
Based on our pilot trial (IRB Protocol # 2015-0323) the E intervention takes about 20-30 minutes following randomization. Once patients are identified for discharge, the wait time before physically leaving the ED provides ample time to consent and complete the initial assessments based on participant randomization at the bedside without adding delays. Participants will be approached for study participation after they have been identified for discharge and BEFORE being physically discharged from the ED.

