### Details of Additional Program

#### Components:

#### ***iCardia & Remote BP***

**Monitoring:** iCardia is a secure password-protected remote monitoring system hosted in a HIPAA-compliant server at UI Health. iCardia provides a user-

friendly environment for authorized personnel to view participants' BP readings in real-time in the form of graphs and send personalized text-messages to participants' cell phones (as needed) through the Twilio communication platform (**Figure 3**). RAs will receive training on iCardia and schedule messages for study participants regarding appointments, medications, and goals. Text messages can be sent immediately, recurrently (e.g. daily), or at a scheduled date/time to one or more participants. All communications utilize Transport Layer Security with encryption.

***Addressing “White Coat HTN”:*** It has been suggested that a “white coat effect” (increase in BP

primarily in the medical care environment) can be present in as many as 20-33% of patients diagnosed with HTN. The use of wireless BP monitors with remote monitoring will address this issue and ensure that this is not a significant confounder in our study population. Following enrollment, subjects will be asked to check their BPs daily.

**Study Coordinator:** The study coordinator will be responsible for overseeing the 48-72 hour HTN outpatient referrals for all study participants and track compliance with follow-up appointments using a combination of EMR review and participant self-report. The study coordinator will also assist with transportation concerns, fax PACTH-c letters to non-UI Health providers, and be trained to use the Open Access scheduling system for selected FQHCs to facilitate appointment scheduling.

**Illinois Video Interpreter Network (IVIN) (all arms):** Translators versed in healthcare terminology are available by video 24 hours a day. In the rare circumstance that a Spanish-speaking study staff member is not available, the IVIN system will be employed to facilitate communication with the participant both at enrollment in the ED and during the PACTH-consultation.

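### Home BP is called a safeguard against low pressure, but the protocol gives no low value or response to one, and its two descriptions set incompatible reading schedules

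*Combined protocol and SAP*

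**What the plan says.** Section 6.0 describes home monitoring twice, and both descriptions end with the same assurance. The text under Figure 1 (Study Design) says "use of the HBPM values will serve as a safety feature to avoid pushing BP too low in study participants". The Smartphone-enabled BP monitoring Kit paragraph, under Details of Intervention Components, says "use of the home BP monitoring values will serve as a safety feature to avoid pushing BP too low in study participants".

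The schedules attached to that assurance differ. Under Figure 1, readings are "preferably daily but a minimum of twice per month", and "In case of missed measurements for 14 consecutive days, participants will be contacted by phone by the RA's". In the kit paragraph readings are daily, and "In case of missed measurements for 7 consecutive days, participants will be contacted by phone by the RA's". The white-coat paragraph, under Details of Additional Program Components, also has participants measuring daily.

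On who looks at the data, the kit paragraph says "All data will be remotely monitored by the RA's through the iCardia platform", and the iCardia paragraph says that authorized staff can "view participants' BP readings in real-time in the form of graphs" and text participants as needed. The only numeric trigger on a home reading is a high one (above 180/120), and it is the participant who must act on it. The notice that accompanies it is "Participants will be informed that the Health Mate app is not a telemonitoring app".

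The PACHT-c paragraph lets the provider start antihypertensives at the ED consultation. Table 1 schedules study BP at months 0, 3 and 6. Table 2 (section 10.0/11.0) lists lightheadedness or passing out, and orthostatic hypotension, among the study-related adverse events.

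**The concern.** A safeguard needs a trigger, someone who looks at known times, and an action. The protocol supplies the person (the RAs) and the display (iCardia), but neither of the other two for a low reading. As written, an RA could watch a run of low values with no stated duty to pass it on.

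The gap falls in the months when it matters most. After the ED visit the next study BP is at month 3, so in arm 2 the home readings are the only scheduled study BP in between. The 48-72 hour referral may produce a clinic BP, but attendance is not assured.

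The schedule conflict is a separate fault. Staff cannot follow both descriptions, and the schedule limits how fast any low-reading rule could work.

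There is also a question of comparability. Arm 2 has extra contacts (texts, and calls after missed readings). If neither arm is asked about low-BP symptoms at fixed times, those symptoms may be noticed more often in arm 2, and the counts in the two arms would not mean the same thing.

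**Working it through.** The plan gives no figure on this point to reproduce, so the check is mainly a side-by-side reading.

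**1. The two schedules**

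| Item | Text under Figure 1 | Kit paragraph |
|---|---|---|
| Readings asked for | daily preferred, two a month as minimum | daily |
| App reminders | daily or bi-weekly | daily |
| Texts start after | 1 week | 3 days |
| Phone call after | 14 days | 7 days |

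The white-coat paragraph agrees with the right-hand column on daily readings.

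**2. Spacing at the minimum**

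- Two readings a month is 24 a year. Evenly spaced, the interval is 365.25 / 24 = 15.2 days.
- That is longer than the 14-day call trigger in the same description. If a missed measurement means a day without a reading, a participant who complies with the minimum can be phoned as non-compliant.
- Over six months the minimum gives 12 readings and the daily schedule about 182, roughly a 15-fold difference.

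**3. What the spacing means for a low spell (illustration)**

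Assume evenly spaced readings and a 7-day spell of low pressure starting at a random time. The chance that at least one reading falls in the spell is min(1, 7 / interval).

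- At the minimum, with every prompt ignored: 7 / 15.2 = 46%.
- If the one-week texts bring a reading about every 8 days (assumed): 7 / 8 = 88%.
- Daily: 100%.

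The first figure is a floor, because daily readings are preferred and the texts begin after a week.

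**4. Search for a low value and a response to it**

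- Figure 1 text and kit paragraph: staff actions are texts and calls, both for missed readings. The one numeric trigger is high and is left to the participant.
- iCardia paragraph: real-time viewing and texting as needed, with no value, review interval or duty to escalate.
- PACHT-c paragraph: starting treatment, but nothing on low readings afterwards.
- Table 2: for hypertensive urgency it names study-visit or clinic BP as the source. It does not mention home readings, and gives no value for low pressure.

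No section of the document supplies the missing rule.

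**5. Symptom questions**

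Table 1 has no symptom or adverse-event row. The call content listed under Assessment of Impact (Aim 3) is PCP follow-up and the Modified Morisky Scale. So no scheduled symptom question is shown for either arm.

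**6. Effect on the trial's size**

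None. The 576 evaluable and 770 enrolled in section 12.0 do not depend on any of this.

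**The case against.** The strongest reply is that the trial is low risk and clinically supervised. Starting medication is optional, guideline-based and decided by a provider; no stepwise study titration is described; a coordinator oversees the referral; and section 10.0/11.0 provides for a DSMB, weekly team meetings and an IRB-approved monitoring plan. The full call script and that plan are not shown and could contain both a low-BP rule and a symptom question. This limits the severity. It does not settle the schedule conflict, and a protocol that makes a safety claim should at least point to the rule behind it.

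Three stronger readings are tempting, and the documents do not support them.

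*That low pressure would go unnoticed for weeks.* Someone with a usual home SBP of 95 mmHg, measured only every 15.2 days, would need about 30 to 46 days (median) to give two consecutive readings below 100, with an assumed within-person SD of 8 to 12. This supposes that every prompt fails. With a reading about every 8 days the median falls to day 16 to 24.

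*That a fixed trigger of 100 mmHg is the answer, at a known workload.* Assume usual SBP averages 130 to 140 and daily readings are independent around each person's usual value. Two consecutive readings below 100 would then flag about 27 to 85 of 385 people by month 3 at a total SD of 21, or 4 to 33 at an assumed SD of 15. Section 12.0 does not tie the 21 to home readings. At SD 21, 63% to 89% of those flagged would have a usual SBP of 100 or more. For example, with mean 130 and within-person SD 12, the between-person SD is sqrt(21² − 12²) = 17.2. The share with usual SBP below 100 is Phi((100 − 130)/17.2) = 4.1%, or about 16 of 385, against 85 flagged. Repeat alerts would run to several hundred at SD 21. These figures argue against a simple two-reading trigger, and the threshold is a clinical choice that the documents do not supply.

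*That adverse-event counts are biased between arms.* Unequal detection is a reasonable inference from unequal contact, but it is not shown. Table 2 applies to any participant, and the unseen script may already ask.

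**Conclusion.** The concern holds in limited form. Two things are established from the text: the safety claim has no low value and no response to a low reading behind it, and the two descriptions of home monitoring cannot both be followed, one of them being at odds with its own call trigger. A third is a sensible precaution: no scheduled symptom question common to both arms is shown.

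The reach is up to 385 arm 2 participants; the number who would start medication is not given. The schedule finding assumes evenly spaced readings and that missed means not taken. The other two rest on what the document prints, with the call script and monitoring plan unseen. Neither a delay in days nor an alert count should be attached as a headline size, since both depend on assumed means and SDs.

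A reader might infer that the SBP comparison is compromised. It is not: no aim tests hypotension, and sample size and primary analysis stand. The point should be dealt with, but as one of safety and adverse-event ascertainment.

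**What to change.** 1. **One schedule.** Keep the kit paragraph's version in both places (daily readings, text after 3 missed days, call after 7), since the white-coat paragraph also says daily. Delete the version under Figure 1.

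2. **Delete the safety sentence in both places, or make it work.** If it is kept, state how often RAs review iCardia and let the study clinicians choose the low-BP criterion. A low multi-day average, or low readings with symptoms, would suit better than any two low values. Allow one open alert per participant. Each alert goes to the PI or a designated study clinician, who contacts the participant and notifies the treating clinician where there is one.

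3. **One symptom question in both arms.** At the existing 1- and 5-month calls and 3- and 6-month visits, ask everyone the same short question on lightheadedness, dizziness on standing and passing out. Orthostatic hypotension is a measured sign and cannot be established by phone, so ask about the symptom. Compare arms on these answers only, and list events found through home readings in arm 2 separately.

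The cost is a short question at contacts already planned, and some clinician time for alerts if the rule is adopted. The rule would become part of the arm 2 intervention and, by prompting some dose reductions, could slightly reduce the SBP difference. No new visits or devices are needed, and the sample size and primary analysis do not change.
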